STUDY PROTOCOL & ANALYSIS PLAN

Protocol Title: A Novel Parent Education Program for Early Intervention
Grant Number: 2U54GM104941-06
Clinical Trials ID: NCT04266717
Date of Document: September 15, 2022

Principal Investigator

Name: [name], PT, PhD
Department/Center: Physical Therapy Department, University of Delaware
Contact [contact]
Email Address: [contact]

PURPOSE

The purpose of this pilot clinical trial is to determine whether parent education impacts daily parent-infant handling and positioning activity or infants' developmental outcomes.

PARTICIPANTS

We will enroll twenty participants 1-5-months-old who are not yet rolling and are of any gender. To be included, infants and their parents must be able to safely and independently engage in the data collection activities and be available for data collections. Infants with medical equipment that restricts movement or positioning will not be included. Infants who are blind will also be excluded. Participants will be recruited via advertisement in the local community.

Participation in the study is voluntary and there is no compensation for participation. During the first contact made with potential participants, written information explaining the study will be provided that details in simple terms, a) criteria for participation, b) purpose of the research and procedures involved, c) right to withdraw at any time without penalty of any kind, and d) assurance of confidentiality (via number ID representation vs. name). If the individual meets the criteria for participation and is interested, the information just described will be reviewed, questions will be answered and an informed consent form will be signed in the presence of a witness. Parents of the participants will be reminded by the researcher that this signature does not bind them to participate and that they are free to withdraw at any time.

PROCEDURES

This study will involve 3 data collections that occur in the home. Informed consent will be obtained prior to the first data collection. Parents will be provided the opportunity to read the consent form, the contents will be reviewed with the family, and any questions or concerns will be discussed prior to obtaining consent.

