After families consent, they will be asked to complete a Health & Demographic Form. Based on the information in this form, infants will be assigned to one of 4 risk categories: No health or socioeconomic risk; Only health risk; Only socioeconomic risk; or Health *and* socioeconomic risk. Health risk will include infants who were born very preterm, infants who had a documented neurologic or respiratory problem at birth, and infants who spent more than 1 week in the neonatal intensive care unit after birth. Socioeconomic risk will include infants whose families report combined income levels below poverty level or report middle or high school completion as the highest level of parental education. Blocked random assignment will then be performed within risk categories so that infants are assigned to the Milestone Education Group or the Positioning Education Group.

The total time commitment for participants in this study involves three data collections 30-75 minutes in duration; the baseline data collection happens at the time families enroll with infants at 1-5 months of age and the second data collection happens one month later. Families will also be asked to allow researchers to contact them monthly to collect milestone attainment data through the time infants begin walking independently (typically occurs between 10 and 18 months of age). The final data collection will happen when infants are between 16 and 24 months of age.

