The first data collection will begin with infants donning the Get Around Garment, a smart garment that collects valid, reliable data about the position of infants (i.e., supine, reclined, upright, inclined, or prone). Then, the data collection will consist of: 1) one 2.5-minute *Structured Play Assessment* during which the infant will be placed by the experimenter for 15-30 seconds into each of the following 5 positions: supine, prone, inclined about 45 degrees from upright, reclined about 45 degrees from upright, and seated upright; 2) one 60 minute *Free Play Assessment* during which parents will be encouraged to go about their typical daily activities as if the experimenter were not there; and 3) a second 2.5-minute *Structured Play Assessment*. Accelerometer data from the garment will be collected simultaneously with video data throughout these assessments. Accelerometer data will be saved on a memory card or transmitted to a research computer via Wi-Fi. The entire visit will be video recorded. By comparing data from the garment and the video throughout the entire visit within each infant, we can determine whether the garment provides valid position data throughout the wearing session. The garment will be left with families, and they will be asked to have their infants wear it for 2 days during awake periods when with an adult but not during periods of sleep or periods without supervision. Families will be asked to log the times the sensor belt was worn and infants' general activity. Sensor data will be stored so we can better understand infants' activity across a typical 2-day period. We will leave 2 garments just in case one gets dirty. We will inform families they can wash the garments as they would typical clothing except that they should first remove the sensor unit. Note that garments that are in good condition (no stains) may be re-used for other babies after we wash them. After the 2-day period, the researchers will collect the garment from the family, will collect the Sensor Wearing Log and ensure the data on the log are complete and correct, and will ask parents to complete the Garment Perception Survey. They will also assess infants using the Alberta Infant Motor Scale and the Bayley Scales of Infant Development III to show their developmental abilities at the start of the study.

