The second data collection will occur after a 4-week period of requested daily activity engagement according to the education received. The researchers will collect the Activity Logs and ensure data on them is complete and correct. Then the researchers will repeat all procedures from the first data collection, as described above, including a second, 2-day wearing period for the garment. Parents will be informed that daily activity engagement is no longer expected. At this data collection, parents will be taught how to keep track of their infant's milestones using the Milestone Checklist. The research team will contact families monthly through the onset of walking (typically between 10-18 months of age) to gather information about infants' performance on this checklist.

The third and final data collection will serve as a follow-up visit when infants are 16-24 months of age. Infants will be assessed using the Alberta Infant Motor Scale to show how their developmental abilities have changed since the start of the study and whether there are differences between the two education groups. Parents will be asked to complete the Dimensions of Mastery Questionnaire (DMQ 18) to evaluate each child's intrinsic motivation to move and explore so we can determine if and how this relates to our early measures of development and interaction.

RISKS AND BENEFITS

The risks associated with participation in this study are minimal. The assessment procedures are safe, and are similar to movement and play activities experienced by infants on a regular basis. The measurements are non-invasive, play- or functionally-based, and have been used in past research with infants.

There is a risk that participants may experience fatigue or be upset during the visits. If the infant cries or shows facial expressions suggesting fatigue or upset, we will take a break from the activities. We will not continue again until the infant has his/her needs met (sleeping, eating, diaper changing, etc) and appears happy and eager to join the testing again based on his/her affect and facial expressions. We will reschedule for another time if that better meets the infant's and family's needs.

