To determine whether changes in parent-child interaction behavior or positioning practices (sensor data) differ from Visit 1 to 2 between the two education groups, Wilcoxon tests will be performed for intra-group, Mann-Whitney for inter-group comparisons, with Bonferroni corrections.

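### The secondary outcomes are compared as unadjusted Visit 1 to Visit 2 changes; adjusting for the Visit 1 value already collected would usually be more precise, unless the two visits are highly correlated

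*Combined protocol and SAP*

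**What the plan says.** The DATA ANALYSIS PLAN gives the secondary outcomes one sentence. Its aim is "To determine whether changes in parent-child interaction behavior or positioning practices (sensor data) differ from Visit 1 to 2 between the two education groups", and its method is "Wilcoxon tests will be performed for intra-group, Mann-Whitney for inter-group comparisons, with Bonferroni corrections". No covariate, baseline-adjusted model or rank ANCOVA is named anywhere in the document.

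The baseline is collected. Under PROCEDURES, the first visit includes "one 60 minute *Free Play Assessment* during which parents will be encouraged to go about their typical daily activities", and the garment then stays with the family: "they will be asked to have their infants wear it for 2 days during awake periods when with an adult". At the second visit, "Then the researchers will repeat all procedures from the first data collection, as described above, including a second, 2-day wearing period for the garment". Each infant should therefore have a Visit 1 and a Visit 2 value of each measure.

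On size and allocation, PARTICIPANTS says "We will enroll twenty participants 1-5-months-old who are not yet rolling", and PROCEDURES says "Blocked random assignment will then be performed within risk categories". The document gives no allocation ratio, block size, alpha, SD or visit-to-visit correlation, and no derivation of the sample size. The primary outcome paragraph applies the same change-score method to AIMS.

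**The concern.** Subtraction fixes the weight on the baseline at exactly 1. Adjustment estimates that weight from the data. If a family's behaviour at Visit 1 predicts its behaviour at Visit 2 only moderately, a weight of 1 is too large and carries Visit 1 noise into the comparison.

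That is plausible here. Positioning is sampled over 2 days and interaction apparently over one hour, about a month apart, in infants who are developing fast. It remains an inference, because the document reports no rho. The description of the garment as valid and reliable concerns its position readings, not how stable a family's habits are. The document also does not say outright that interaction is scored from the 60-minute free play; that is a reasonable reading of PROCEDURES.

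The PURPOSE section has two halves, daily handling and positioning, and infant development. This paragraph is the only planned analysis of the first half, and PROCEDURES presents the measurement of everyday positioning as what is new in the trial. With 20 infants and a Bonferroni correction of unstated size, avoidable loss of precision is worth recovering.

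**Working it through.** There is no sample-size or power figure in the plan to reproduce, so the check compares the planned analysis with the alternative.

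**Inputs.** From the document: 20 infants; change scores; Mann-Whitney between groups. Assumed: 10 per group, equal SDs at both visits, normal data, a true difference of 1 Visit 2 SD, two-sided 0.05 without Bonferroni, and rho from 0.3 to 0.9.

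**Step 1: variance per infant, in units of SD².**
- Change score: 2(1 − rho)
- Visit 2 alone: 1
- Visit 2 adjusted for Visit 1: 1 − rho²

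The ratio of adjusted to change is (1 − rho²) / [2(1 − rho)] = (1 + rho)/2. The change score is noisier than Visit 2 alone when 2(1 − rho) > 1, that is, when rho < 0.5. At rho 0.3 the three variances are 1.4 (change), 1.0 (Visit 2 alone) and 0.91 (adjusted).

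**Step 2: the price of estimating the slope.** At N = 20 the adjusted variance is multiplied by 1 + 1/(20 − 4) = 17/16.

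| rho | Large-sample ratio | Ratio at N = 20 |
|---|---|---|
| 0.3 | 0.65 | 0.69 |
| 0.5 | 0.75 | 0.80 |
| 0.7 | 0.85 | 0.90 |
| 0.8 | 0.90 | 0.96 |
| 0.9 | 0.95 | 1.01 |

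Break-even is at (1 + rho)/2 × 17/16 = 1, so rho = 32/17 − 1 = 0.88.

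**Step 3: power.** The Mann-Whitney and linear-model columns are simulated; repeated runs agreed to within about 2 points. The t-test column follows from the non-central t distribution with 18 df and non-centrality 1 / [√(2(1 − rho)) × √(2/10)], which is 1.89, 2.24, 2.89 and 3.54 at the four values of rho.

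| rho | Mann-Whitney on change (planned) | t test on change | Linear model adjusted for Visit 1 |
|---|---|---|---|
| 0.3 | 38% | 43% | 57% |
| 0.5 | 51% | 56% | 66% |
| 0.7 | 73% | 78% | 81% |
| 0.8 | 89% | 92% | 93% |

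Mann-Whitney on Visit 2 alone gives about 51%. The step from the first column to the second, about 4 to 5 points at rho 0.3 to 0.7, is the move from a rank test to a parametric one. Only the step from the second to the third comes from using the baseline better: 14, 10, 3 and 1 points.

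**Step 4: error rate.** Simulated type I error was 4.0% to 4.6% for Mann-Whitney on change and 4.6% to 5.4% for the adjusted model, so the gain does not come from a loose test. With a permutation p-value, the adjusted model's power was 57%, 65% and 81% at rho 0.3, 0.5 and 0.7.

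**Step 5: other data shapes (assumed).** Mann-Whitney on change v linear adjustment, untransformed:
- Lognormal: 61% v 69% at rho 0.3, 72% v 75% at 0.5, 87% v 85% at 0.7, 94% v 91% at 0.8.
- Heavy-tailed (t with 3 df): 56% v 69% at rho 0.3, 88% v 86% at 0.7, 96% v 93% at 0.8.
- A second strongly right-skewed shape: 55% v 53% at rho 0.5, 74% v 67% at 0.7.
- Bounded, proportion-like: 44% v 61% at rho 0.5.

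Rank ANCOVA is unaffected by monotone transformation. Under the second skewed shape it gives 54–55% against 43% for change at rho 0.3, and 61–63% against 55% at rho 0.5. With normal data it gives 75% against 73% at rho 0.7, but 97% against 99.5% at rho 0.9.

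**The case against.** The strongest reply is that the planned analysis is valid. Under randomisation a comparison of changes is unbiased, and its error rate is controlled. The trial is a pilot with no stated power target, and a rank test is a natural choice at this size. For a difference of 0.5 SD at rho 0.5, power is about 16% planned against 22% adjusted, which is inadequate either way. All of this stands, and it makes the point one of efficiency.

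Four stronger readings are tempting, and none is supported:
- A reader might infer that the change-score result would be wrong. It would be less precise, not biased.
- A reader might take it as established that the baselines are noisy. The document gives no visit-to-visit correlation, so the loss could be large, small or nil.
- A reader might say that the plan gives up a third of its attainable power for nothing. That is only the rho 0.3 corner (38/57 = 0.67). Like for like it is about a quarter (43/57 = 0.75), and the rank test has real advantages with skewed data.
- A reader might hold that adjustment wins at every rho below 1. That is a large-sample statement; with 20 infants the advantage ends near 0.88.

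It is also fair to object that changing only the secondary paragraph would leave two between-group methods in a very short plan. The fix therefore extends to AIMS.

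**Conclusion.** The point holds as a matter of efficiency. The plan uses a baseline it already collects in a way that is less precise than adjustment for rho below about 0.88 at this sample size, and less precise than ignoring baseline for rho below 0.5.

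Under the stated assumptions, adjustment lowers the variance by about 31% at rho 0.3, 20% at 0.5 and 10% at 0.7. The power gain over the planned test is 19, 15 and 8 points respectively, including the 4 to 5 points due to the change of test family. At rho 0.8 the gain is about 4 points, nearly all of it from that change.

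The formulas are firm. The size is not, because rho, the SDs, the data shape and the Bonferroni family are all missing from the document, and any Bonferroni correction would lower every power figure.

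**What to change.** In the Secondary outcomes paragraph, replace the between-group Mann-Whitney on change with a comparison of the Visit 2 value adjusted for the Visit 1 value of the same measure. Modelling the change with the Visit 1 value as covariate gives the identical group effect and p-value, so the plan can keep its wording about change.

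- **Form.** Fix it before unmasking: a linear model, with a transformation set in advance if the measure is skewed, or rank ANCOVA.
- **P-value.** Use a permutation test that re-randomises within the risk categories and blocks actually used. Free shuffling of labels across all 20 infants would not match the allocation. The document does not give the block sizes, so these must be recorded.
- **Estimate.** Report the adjusted difference between groups.
- **Consistency.** Consider the same adjustment for the primary AIMS comparison, which uses the same change-score method.

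The cost is a sentence of plan text and a few lines of code, with no new data or visits. The downside is little or no gain, or a loss of a few points of power, when rho is about 0.8 or more. With strongly skewed, untransformed data the linear model can lose about 2 to 7 points at rho 0.7, and in one assumed shape it gained nothing at 0.5. Rank ANCOVA or a pre-set transformation is the safeguard there, though rank ANCOVA itself falls 2 to 3 points short of the planned test at rho 0.8 or more with normal data.

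### Does rolling that begins between the two garment wears undermine the sensor analysis of positioning?

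*Combined protocol and SAP*

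**What the plan says.** - PARTICIPANTS sets the entry rule: "We will enroll twenty participants 1-5-months-old who are not yet rolling". RISKS AND BENEFITS repeats it as a bar to enrolment. Neither section extends it to later visits.
- PROCEDURES gives the interval: "the second data collection happens one month later". All first-visit procedures are then repeated, including the 2-day home wear.
- The garment yields data on "the position of infants (i.e., supine, reclined, upright, inclined, or prone", that is, five categories of infant position. At home, families are asked to have infants "wear it for 2 days during awake periods when with an adult but not during periods of sleep or periods without supervision". For the log: "Families will be asked to log the times the sensor belt was worn and infants' general activity". For the visit itself: "The entire visit will be video recorded".
- When the garment is collected after the 2-day wear, the Alberta Infant Motor Scale (AIMS) and Bayley III are administered. Because first-visit procedures are repeated, this also happens after the second wear. Families are taught the Milestone Checklist at that visit.
- PURPOSE includes "to determine whether parent education impacts daily parent-infant handling and positioning activity". In its account of the education, PROCEDURES presents the garment as the means of measuring how education affects caregivers' everyday positioning.
- DATA ANALYSIS PLAN, Secondary outcomes, asks whether changes in "positioning practices (sensor data) differ from Visit 1 to 2 between the two education groups, Wilcoxon tests will be performed for intra-group" comparisons, with Mann-Whitney tests for the comparison between groups.

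**The concern.** The sensor measures the infant, while the plan's language points to the parent. An infant who is placed supine and rolls to prone produces the same record as one whom a parent places prone. Infants enter at 1-5 months and wear the garment again at about 2-6 months, so some may have started to roll.

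Two readings are then exposed. A within-arm change from Visit 1 to Visit 2 mixes caregiver behaviour with maturation, and randomisation does not protect a before-after comparison inside one arm. A between-arm difference could be credited to parents when it reflects infants' own mobility, if rolling differs by arm. The plan states no limit on interpretation and does not link any record of rolling to the sensor outcome. At stake is a claim that parents changed how they position their infants, which is part of the trial's stated purpose.

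**Working it through.** The plan gives no alpha, effect size or rolling rate, so it has no figure to reproduce. The check has a textual part and an illustration.

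**1. Age at the second wear.** 1-5 months + 1 month = 2-6 months. New rolling is possible; its frequency is not in the documents.

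**2. What each test addresses.** The Mann-Whitney test compares change scores between randomised arms. The Wilcoxon test asks whether position changed within an arm. Neither null hypothesis mentions who caused the change.

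**3. Illustration.** Assumptions, none from the documents except the total of 20 infants:
- 10 infants per arm and no change in caregiver behaviour;
- change score = N(0,1) + d for each infant who rolls, with d = 0.5, 1 or 2 SD;
- rolling drawn at random for each infant;
- exact two-sided tests, 40,000 trials per scenario. The simulation standard error near 5% is √(0.05 × 0.95 / 40,000) = 0.11 percentage points.

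| Test and rolling rate | Level | d = 0.5 | d = 1 | d = 2 |
|---|---|---|---|---|
| Within arm, 30% | 0.05 | 6.9% | 11.1% | 20.4% |
| Within arm, 30% | 0.01 | 1.5% | 2.9% | 5.6% |
| Between arms, 30% v 30% | 0.05 | 4.3% | 4.3% | 4.4% |
| Between arms, 10% v 30% | 0.05 | 4.6% | 5.9% | 8.3% |
| Between arms, 10% v 30% | 0.01 | 1.0% | 1.5% | 2.2% |

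The 0.01 level is 0.05/5, a Bonferroni correction if the family were the five positions; the plan does not state the family size. A wider imbalance does more: in a separate run of 4,000 trials at 0.05, rolling rates of 60% v 20% with d = 2 gave 23% between arms.

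**4. Chance imbalance.** With a 30% rolling rate in both arms, the realised counts differ by 2 or more in 46% of trials. The between-arm test still rejects in only 4.3-4.4%, because that variation is already part of its error rate. Only a true difference in rolling rates moves it. With randomised arms, such a difference would itself be an effect of the education on infant position.

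**5. What a rolling record could show.** A split of 1/10 v 3/10 has two-sided Fisher p = 0.58, and even 1/10 v 6/10 has p = 0.057. Combining the lying positions does not help. If rolling turns 15 of 60 supine minutes into prone minutes, supine changes by -15, prone by +15 and their sum by 0. A caregiver who moves the same 15 minutes from supine to prone gives the same three figures.

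**The case for a change.** The best argument for a change is that the plan itself treats rolling as a stage boundary at entry and then ignores it a month later, in a trial that presents the garment as its window on caregiver behaviour. One form item, one count by arm and a sentence of caution would cost little. Video covers the visit and not the home wear, and the log is described only as wear times and general activity. A sentence in the report claiming that parents changed, drawn from a within-arm p-value, would be unsupported.

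That last point stands as advice on reporting. The rest is weaker. Nothing in the plan says the within-arm results will be read that way. The plan's question, and its description of the garment as measuring the impact of education, both concern an effect between arms. Nor is it shown that rolling goes unrecorded: AIMS and Bayley III are repeated when the garment is collected after the second wear, the Milestone Checklist begins at that visit, and the visit is filmed. The documents do not list the items of these instruments, so they prove neither that rolling is captured nor that it is missed.

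The within-arm figures also carry less than they seem to. They count a rejection as an error against a null of no caregiver change, whereas the Wilcoxon test concerns change in position, which did occur. They would be the same for any maturational shift of that size. What remains is the familiar limit of uncontrolled before-after change, which applies equally to the within-arm tests of AIMS and parent-child interaction.

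**Conclusion.** No change to the plan is needed. The randomised sensor comparison is valid for the effect of education on infant position. Attributing a difference to caregivers is open only if infants' own mobility differs by arm, which the documents do not establish. Under the assumptions above, equal rolling leaves the between-arm test at 4.3-4.4% at 0.05. Rates of 10% v 30% raise it to at most 8.3%, and 60% v 20% with a 2 SD shift to 23%. Those rates and shifts are assumed, so the figures show direction and not likely size.

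A competent analyst closes the gap in the write-up: call the outcome infant position, rest the conclusion on the between-group test, treat the within-group results as descriptive, and mention rolling status if the Visit 2 assessments or video show it. None of this alters a test, an estimate or who is analysed. A breakdown by rolling in arms of about 10 could not settle who moved the infant. The point touches a secondary outcome in a 20-infant pilot and leaves the primary AIMS comparison as it is.

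### The secondary between-group tests use Bonferroni at about 10 infants per arm; Holm keeps the same familywise error and is never less powerful, for a small gain

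*Combined protocol and SAP*

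**What the plan says.** The Purpose asks first whether parent education "impacts daily parent-infant handling and positioning activity", and then about developmental outcomes. Under Participants: "We will enroll twenty participants 1-5-months-old who are not yet rolling and are of any gender". Under Procedures, "Blocked random assignment will then be performed within risk categories" to one of two education groups. The allocation ratio is not given.

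Also under Procedures, the garment classifies infant position as "supine, reclined, upright, inclined, or prone". At the first data collection, and again at the second, families are asked to have the infant "wear it for 2 days during awake periods when with an adult".

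Under Data Analysis Plan, Secondary outcomes, the question is whether "changes in parent-child interaction behavior or positioning practices (sensor data) differ from Visit 1 to 2" between the two education groups. The method is Wilcoxon within groups and "Mann-Whitney for inter-group comparisons, with Bonferroni corrections". The section does not state the positioning measure, its scale, the alpha level, or the number of tests that the correction divides by.

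**The concern.** Bonferroni tests every hypothesis at alpha divided by the number of tests, even after some have been rejected. Holm starts at that same threshold and relaxes it after each rejection. Both control the familywise error under any dependence between the tests. Anything Bonferroni rejects, Holm rejects too. Keeping Bonferroni therefore gives up some power without better error control.

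This applies to positioning practice, the first aim in the Purpose and the outcome the garment was brought in to measure, in a trial of about 10 infants per arm. The loss grows with the number of tests in the family, and the plan leaves that number open. At least two outcomes are named. If each of the five garment positions were tested, the divisor would be larger.

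**Working it through.** The plan states no power, alpha or effect size, so it has no figure to reproduce. All results below are conditional on assumptions.

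**Inputs**
- From the documents: 20 infants, two arms, Mann-Whitney, Bonferroni, at least two secondary outcomes, five garment positions.
- Assumed: 10 per arm; two-sided familywise 0.05; normally distributed changes with a standardised difference d between arms.

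**One Mann-Whitney test, 10 per arm.** These are simulated normal shifts (40,000 replicates) with exact critical values: U ≤ 23 for 0.05, U ≤ 20 for 0.025, U ≤ 16 for 0.01.

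| d | at 0.05 | at 0.05/2 = 0.025 | at 0.05/5 = 0.01 |
|---|---|---|---|
| 0.5 | 16% | 11% | 5% |
| 0.8 | 35% | 26% | 15% |
| 1.0 | 51% | 41% | 26% |
| 1.5 | 85% | 78% | 64% |

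**Holm against Bonferroni, two outcomes.** Bonferroni rejects outcome 1 if p1 ≤ 0.025. Holm also rejects it if 0.025 < p1 ≤ 0.05 and p2 ≤ 0.025. With independent outcomes, both at the same d:

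Holm power = P(p1 ≤ 0.025) + [P(p1 ≤ 0.05) − P(p1 ≤ 0.025)] × P(p2 ≤ 0.025)

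- d = 1.0: 0.406 + (0.513 − 0.406) × 0.406 = 0.406 + 0.043 = 0.449. Power per outcome goes from about 40% to 45%.
- d = 0.8: 0.258 + (0.352 − 0.258) × 0.258 = 0.258 + 0.024 = 0.282. Power per outcome goes from about 26% to 28%.

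**Holm against Bonferroni, five shares.** Suppose the five positions were analysed as shares of wear time that sum to 100%, with one share up by d = 1.0 and the other four down evenly. Simulated power at 0.01 is 0.264 for the first share and 0.018, 0.017, 0.020 and 0.016 for the others. These sum to 0.335, so Bonferroni gives about 0.34 rejections per trial. Holm gives about 0.35. The chance of at least one rejection is identical, because both procedures start at 0.01.

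**Optional step: one pre-named positioning measure.** Suppose all five positions would otherwise be tested at 0.01.

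| Comparison | d = 0.8 | d = 1.0 |
|---|---|---|
| Named position, tested at 0.05 | 35% | 51% |
| Named position, tested at 0.025 (interaction stays in the family) | 26% | 41% |
| Same position, at 0.01 | 15% | 26% |
| Any of five at 0.01, time drawn evenly from the other four | 19% | 31% |
| Any of five at 0.01, time drawn from one other position | 28% | 45% |
| Wrong position named, at 0.05 | about 4–6% | about 4–7% |

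Against the same position at 0.01, a full 0.05 gives 35/15 = 2.3 times the power at d = 0.8 and 51/26 = 2.0 times at d = 1.0. Against any-of-five, the ratio is 35/28 = 1.25 to 35/19 = 1.8 at d = 0.8, and 51/45 = 1.1 to 51/31 = 1.6 at d = 1.0. At 0.025 the named measure (26%, 41%) falls slightly below any-of-five when the time comes from a single other position (28%, 45%).

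**The case against.** A reader might infer something stronger: that the plan splits alpha over five redundant shares of wear time, and that one named summary at 0.05 would roughly double the power. The documents do not support that.

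- They list five positions the garment can classify. They do not say that five measures are tested, that these are shares, or that the divisor is 5. The sponsor may intend a single measure.
- The doubling holds only for divisor 5, d near 0.8 to 1.0, and a comparison of one position with itself. At d = 0.5 the ratio is about 3.1, and at d = 1.5 about 1.3. A plan that tests five positions can succeed on any of them, and against that the gain is smaller.
- The content of the positioning handout is not in the documents, so which position would carry the effect is unknown. A wrong choice leaves almost no power.
- A full 0.05 for one sensor measure takes parent-child interaction and the within-group tests out of the family. That loosens error control and would have to be stated openly.

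These objections stand, and they make the single lead measure a matter for the sponsor's judgement.

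Against Holm, one can say that Bonferroni comes with simple matching simultaneous confidence intervals and Holm does not. That is true, but the plan promises no such intervals. One can also say that the gain is trivial in a pilot's secondary outcomes. It is small, but it costs nothing in error control. Holm does not change the chance of a first rejection, so it does not make up for the small sample.

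**Conclusion.** The point holds as a minor improvement. The plan states Bonferroni for the secondary between-group tests, and Holm over the same family is at least as powerful with the same familywise error. That statement needs no assumption about effects or correlation.

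Its size does need assumptions (10 per arm, two-sided 0.05, normal shifts). It is about 5 percentage points per outcome when two independent outcomes both have d = 1.0, about 2 points at d = 0.8, and about 0.01 extra rejections per trial over five shares.

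Naming one positioning measure could add more, but only if that measure carries the effect and only at the alpha actually left to it. Even at a full 0.05, 80% power needs d of about 1.4 or more, so neither change makes this trial well powered for positioning.

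**What to change.** Under Data Analysis Plan, Secondary outcomes, replace Bonferroni with Holm for the between-group Mann-Whitney tests. State in the same sentence which tests form the family, since neither procedure can be run without that count. The cost is one sentence, with no new data. What is given up is simple matching simultaneous intervals, which the plan does not offer.

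Optionally, and before unmasking, the sponsor may name one positioning measure (a position or a sum of positions) that its own handout is mainly meant to change, and state the alpha for it. Keeping parent-child interaction in the family means 0.025 for a Bonferroni split over the two outcomes, or Holm over both. Using 0.05 requires saying that interaction and the within-group tests lie outside the family. The cost is that a change confined to another position becomes supportive only, and a sum of positions dilutes the effect if only one of them moves.
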